• IV immunoglobulin (IVIG) ~1000 mg/kg administration – initiate only if immunoglobulin levels fall below 500 mL/dL. Dose will be adjusted to maintain serum trough levels of 500-1000 mg/dL. Will occur after vector infusion.

Day 15, Day 22:

- Continuation of sirolimus*, prednisolone, and lansoprazole dosing (PO or by feeding tube)
 - *adjustment permitted to achieve trough levels of 7-12 ng/mL
- Continuation of trimethoprim/sulfamethoxazole 2.5 mg/kg/day BID on 2 consecutive days per week (PO or by feeding tube) or per PI discretion

Week 4/Month 1:

- Continuation of sirolimus*, prednisolone, and lansoprazole dosing (PO or by feeding tube)
 - *adjustment permitted to achieve trough levels of 7-12 ng/mL
- Continuation of trimethoprim/sulfamethoxazole 2.5 mg/kg/day BID on 2 consecutive days per week (PO or by feeding tube) or PI discretion
- IVIG ~1000 mg/kg if IgG levels are below 500 mL/dL. Dose will be adjusted to maintain serum trough levels of 500-1000 mg/dL.

Week 6, Week 8, Week 10:

- Continuation of sirolimus*, prednisolone, and lansoprazole dosing *adjustment permitted to achieve trough levels of 7-12 ng/mL
- Continuation of trimethoprim/sulfamethoxazole
- IVIG \sim 1000 mg/kg if IgG levels are below 500 mL/dL. Dose will be adjusted to maintain serum trough levels of 500-1000 mg/dL.

Week 12/Month 3 to Week 20/Month 5:

- Initiate prednisolone tapering regimen:
 - Week 12-13: Reduce Dose by 50%
 - Week 13-14: Reduce week 12-13 Dose by 50%
 - Week 14-15: Reduce week 13-14 Dose by 50%
 - Week 15-16: Reduce week 14-15 Dose by 50% then stop
- Lansoprazole to be discontinued following completion of prednisolone tapering
- Continuation of sirolimus*
 - *adjustment permitted to achieve trough levels of 7-12 ng/mL
- Continuation of trimethoprim/sulfamethoxazole
- IVIG \sim 1000 mg/kg if IgG levels are below 500 mL/dL. Dose will be adjusted to maintain serum trough levels of 500-1000 mg/dL.

Week 24/Month 6

• Initiate weaning of sirolimus:

Confidential Page 41 of 97

Clinical Study Protocol: AXO-GM2-001

Version 8.0, 09 June 2023

- Week 24-25: reduce dose by 50% (PO or by feeding tube)
- Week 25-26: reduce Week 24-25 dose by 50% (PO or by feeding tube)
- Week 26-27: reduce Week 25-26 dose by 50% (PO or by feeding tube) then stop
- Trimethoprim/sulfamethoxazole to be discontinued following completion of sirolimus wean

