The ITI regimen will be stopped upon evidence of any of the following severe conditions for which no other cause has been identified: (1) intractable, severe opportunistic infections, not able to be managed with antibiotic, antifungal or antiviral therapy; (2) renal dysfunction (rising creatinine or BUN); (3) severe rash; (4) evidence of CNS problems including seizures or encephalopathy; (5) bleeding or clinically significant elevation of bleeding parameters.

Participants requiring discontinuation of the ITI regimen prior to Visit 1a (Day 1) will not be eligible for gene transfer and will be withdrawn from the study.

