8.3.2. Immune Tolerance Induction (ITI) Regimen Justification

The prophylactic ITI regimen will be administered starting 7 days prior to gene transfer and will continue to week 24 to prevent antibody response to AAV capsid in participants receiving gene therapy. The potential for immune modulation to prevent antibody response to AAV capsid in participants receiving gene therapy was demonstrated by Corti et. al following a trial of intra-diaphragmatic injection of AAV1-GAA in participants with infantile Pompe disease (Corti et al. 2017). Three CRIM negative participants receiving AAV1-hGAA had also received chronic immune modulation with rituximab and sirolimus due to pre-existing immune responses to enzyme replacement therapy (ERT). These participants had no immunologic response to AAV capsid proteins or the GAA protein. This was in contrast to the 5 CRIM positive participants who had not received immune modulation and had an average 150-fold increase in anti-AAV1 titer after exposure to AAV1.

Immune modulation using rituximab has become the therapy of choice for CRIM negative infants to maintain the efficacy of ERT (Elder 2013, Kazi 2017).

A similar mitigation of antibody response to AAV9 capsid and therapeutic protein has been observed in an expanded access trial of intravenous plus ICV administration of rAAV9-hASPA

Confidential Page 43 of 97

UMass Chan Medical School Clinical Study Protocol: AXO-GM2-001

Version 8.0, 09 June 2023

transgene in a child with Canavan disease (Corti et al. 2018). In this study with rituximab and sirolimus preconditioning, the immune response was abrogated.

In another ongoing trial, "Re-administration of Intramuscular AAV9 in Subjects with Late-Onset Pompe Disease," (NCT02240407, IND #17404) a similar immune modulation strategy to ablate B- and T-cells (rituximab, sirolimus, methylprednisolone and prednisone) prior to the initial exposure to AAV9 by intramuscular injection prevented the formation of antibody against AAV9 and the GAA transgene.

The ITI regimen was administered and well-tolerated in the two TSD subjects that are part of an ongoing Expanded Access clinical trial for AAVrh8-*HEXA/HEXB* gene therapy (IND# 18225).

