8.7. Potential Risks

The risks of administering AXO-AAV-GM2 treatment in TSD or SD participants are not completely known. There are theoretical/potential risks with AXO-AAV-GM2, certain known risks associated with BiTh and ICM/IT administration of AXO-AAV-GM2, and there are certain known risks associated with the proposed ITI regimen. These risks are described in the Investigator's Brochure.

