8.8. Criteria for Study Termination

The study stopping criteria are outlined in Section 9.4. In the event of a stopping criteria event, the DSMC and Sponsor will be notified for determination of significant safety risks (as outlined in the DSMC Charter).

Confidential Page 53 of 97

Clinical Study Protocol: AXO-GM2-001

Version 7.0, 09 June 2022

 Table 14:
 Schedule of Juvenile-Onset Participant Assessments

Schedule of Activities	Visit A	Visit B	Visit C	Visit D	Visit 1a	Visit 1b	Visit 2	Visit 3	Visit 4	Visit 5	Visit 6	Visit 7	Visit 8	Visit 9	Visit 10	Visit 11	Visit 12	Visit 13	Visit 14	Visit 15
	Week	Day	Day	Day	Day	Day	Day	Day	Day	Week	Week	Week	Week	Week	Week	Week	Week	Week	Week	Week
	- 8 ±28d	-16 ±5d	-7 ±3d	-2 ±1d	1 -	2	8 ±1d	15 ±3d	22 ±3d	4 ±3d	6 ±4d	8 ±5d	10 ±4d	12 ±7d	16 ±7d	20 ±7d	24 ±7d	48 ±7d	72 ±7d	96 ±7d
ICF	X*	X					-14		250					274			±/u	±/u		±/ u
Inclusion/Exclusion Criteria	X*	Х																		
Genetic Confirmation ¹	X*																			
Vital Signs ²	X*	X	X	X	X	X	X	X	X	X	X	X	X	X			X	X ²⁷	X ²⁷	X ²⁷
Weight	X*	X	X	X			X	X	X	X	X	X	X	X			X	X ²⁷	X ²⁷	X ²⁷
Height	X*	X	X											X			X	X ²⁷	X ²⁷	X ²⁷
Physical Examination	X*			Х	X	X	Х	X	X	Х	Х	Х	Х	X			X	X ²⁷	X ²⁷	X ²⁷
Neurologic Examination ³	X*			X		X	X	Х	X	X	Х	Х	Х	X			X	X ²⁷	X ²⁷	X ²⁷
Tele-health follow-up call															X	X		X ²⁸	X ²⁸	X ²⁸
Tele-health Neuro Exam																		X^{28}	X ²⁸	X ²⁸
Ophthalmology Exam			X																	
Urinalysis					X									AN			AN	AN	AN	AN
Participant Appropriate Neuro-Cognitive Assessments ²²	X*									X				Х			X	X ²⁷	X ²⁷	X ²⁷
Clinical Global Impression ²³	X*									X				X			X	X	X	Х
Motor Assessments ²⁴	X													X			X	X ²⁷	X^{27}	X^{27}
BAER/VER/SSEP ²⁶	X													X			X	X ²⁷		
CBC with auto-differential ⁴	X				X	X	X	X	X	X	X	X	X	X			X	X ²⁷	X 27	X ²⁷
Comprehensive metabolic panel ⁴	X				X	X	X	X	X	X	X	X	X	X			X	X 27	X ²⁷	X 27
CRP	X				X	X	X	X	X	X	X	X	X	X			X	X ²⁷	X ²⁷	X ²⁷
GGT – AN due to elevated liver enzymes	AN				AN	AN	AN	AN	AN	AN	AN	AN	AN	AN			AN	AN	AN	AN
PT, PTT, INR, Blood Typing ⁴				Х																
CD 19, 20 count		X	X	Х		AN				X		X		X			X	X 27	AN	AN
IgA level			X																	
IgG levels ⁶				X						X		X		X			X	AN	AN	AN

Confidential Page 54 of 97

Clinical Study Protocol: AXO-GM2-001

Version 8.0, 09 June 2023

 Table 14:
 Schedule of Juvenile-Onset Participant Assessments (Continued)

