9.4. Study Stopping Criteria

Temporary suspension of enrollment and administration of AXO-AAV-GM2 to study participants will result if any of the following occur in the study:

- 1. Death of any participant in which the cause of death is assessed by the investigator as at least possibly related to the AXO-AAV-GM2 or the neurosurgical administration procedure.
- 2. Intracranial hemorrhage related to the BiTh procedure or an event suggestive of or consistent with craniospinal herniation related to the ICM/IT procedure.
- 3. Two or more CTCAE Grade 3 or higher adverse events in any participant that are assessed by the investigator as possibly, probably or definitely related to AXO-AAV-GM2 or the neurosurgical administration procedure

Confidential Page 70 of 97

Clinical Study Protocol: AXO-GM2-001

Version 8.0, 09 June 2023

4. An SAE in any participant where the event is assessed by the investigator as possibly, probably or definitely related to AXO-AAV-GM2 or the neurosurgical administration procedure

The DSMC will review all available safety data for AXO-AAV-GM2 and the neurosurgical administration/infusion procedures and will make recommendation(s) regarding further study conduct. The DSMC may make a recommendation regarding dose de-escalation/escalation. The clinical study may resume after appropriate steps are taken to address these AEs, including revision of the clinical protocol. Any participants who have already received IMP and are currently in the study at the time study stopping criteria are met will continue to be followed-up, for safety and any signs of efficacy, per protocol.

Confidential Page 71 of 97

Version 8.0, 09 June 2023

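### No stopping criterion in Section 9.4 covers a death attributed solely to the mandated immunosuppression regimen: a narrow gap, cheap to close

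*Combined protocol and SAP*

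**What the plan says.** Section 9.4 lists four events with one consequence: "Temporary suspension of enrollment and administration of AXO-AAV-GM2 to study participants will result if any of the following occur". Criterion 1 counts a death only if its cause "is assessed by the investigator as at least possibly related to the AXO-AAV-GM2 or the neurosurgical administration procedure". Criteria 3 and 4 (two or more Grade 3 events in a participant; any SAE) require relatedness to the same two sources. Criterion 2 covers hemorrhage from the thalamic procedure and herniation from the cisternal/intrathecal procedure. Once a criterion is met, "The DSMC will review all available safety data for AXO-AAV-GM2 and the neurosurgical administration/infusion procedures"; ITI is not named there. The footnote to Table 18 (Section 10.1) defines AXO-AAV-GM2 as the two vectors combined, so the immunosuppressive drugs are not part of it.

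ITI is mandatory. Section 8.3.2 states: "The prophylactic ITI regimen will be administered starting 7 days prior to gene transfer". The sirolimus wean in Section 8.2 ends with "Week 26-27: reduce Week 25-26 dose by 50% (PO or by feeding tube) then stop". Section 8.7 treats the regimen as a risk source separate from the vector and its administration: "there are certain known risks associated with the proposed ITI regimen".

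Two other sections come close to a rule. Section 8.2 stops ITI for listed severe conditions and adds "Participants requiring discontinuation of the ITI regimen prior to Visit 1a (Day 1) will not be eligible for gene transfer"; this acts on the affected child. Section 8.8 refers back to 9.4 and says that, when a stopping criterion is met, "the DSMC and Sponsor will be notified for determination of significant safety risks (as outlined in the DSMC Charter").

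**The concern.** The plan names three sources of risk (vector, neurosurgical delivery, ITI) and ties its automatic hold to the first two. Two non-serious Grade 3 events possibly related to the vector in one child would suspend the study without anyone having to decide. A child's death attributed only to the mandated regimen would not. The protocol gives no reason for the difference.

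At stake is the next child. That child receives the same drugs, and after such a death a pause depends on someone choosing to impose it. Section 13.9.1.1 already counts events caused by a protocol-mandated intervention before treatment as adverse events, but no stopping criterion uses them.

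**Working it through.** The plan gives no figure to reproduce. The check applies each criterion to one test event, then counts who could proceed without an automatic hold.

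**Step 1. Test event: a death attributed only to ITI, with vector and neurosurgery excluded.**

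| Criterion in 9.4 | What it requires | Met? |
|---|---|---|
| 1. Death | at least possible relation to vector or neurosurgical procedure | No |
| 2. Hemorrhage or herniation | relation to the thalamic or cisternal/intrathecal procedure | No |
| 3. Two or more Grade 3+ events | at least possible relation to vector or neurosurgical procedure | No |
| 4. SAE | at least possible relation to vector or neurosurgical procedure | No |

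Criteria met: 0 of 4.

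**Step 2. Does another section supply the hold?** Section 8.2 acts on the individual child. The notification in 8.8 depends on a 9.4 criterion having been met. Section 13.10 lets causality be assigned to a study procedure, but 9.4 uses only the neurosurgical one. Section 17.1 has the DSMC notified of all SAEs and able to recommend changes; that is an alert and a recommendation. The protocol therefore contains no automatic hold for this event.

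**Step 3. Death on ITI before Day 1.**
- Length: 7 days. With the Day -7 ± 3-day window in Tables 14 and 15: 7 − 3 = 4 to 7 + 3 = 10 days.
- Attribution: neither vector nor neurosurgery has been given, so neither can be the cause.
- Other children released: under sequential release the child who dies is the released child, so 0 others. Where the Synopsis allows an infantile and a second juvenile participant to be treated concurrently (Mid and High cohorts), 1.
- What is missing: mainly the enrollment hold before the next release. The Synopsis and Section 8.1.1 word that review around dosed participants, and this child was never dosed. Section 8.1.1.1 refers to all previous participants, which would include the child.

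**Step 4. Death in a child already dosed, up to about Week 27.**
- Time from release to dosing: the footnotes to Tables 14 and 15 require DSMC and Sponsor approval before the Visit A tests that carry no asterisk, at Week -8 ± 28 days. On schedule that is 8 × 7 = 56 days, with a range of 56 − 28 = 28 to 56 + 28 = 84 days (4 to 12 weeks).
- Overlap: release uses the previous child's Week 4 data, so the next child is dosed when the previous one is at about Week 4 + 4 = 8 to Week 4 + 12 = 16, still on sirolimus. ITI lasts 1 + 27 = 28 weeks, of which 27 − 4 = 23 (82%) follow the Week 4 data.
- Released children who could start ITI or be dosed without an automatic hold: 1, or 2 with concurrent treatment.
- Condition: the investigator must exclude vector and procedure even as possible causes. The documents do not show how often that would happen.

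**Step 5. After the change.** With ITI named in criterion 1, the test event meets 1 of 4 criteria and the existing suspension applies. Sample size and analysis are unaffected.

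**The case against.** The case against has force on several points.

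- **The two scenarios must be kept apart.** A reader might infer that one or two released children are exposed in the clear case, before Day 1. The release sequence does not support that: the count there is 0, or 1 with concurrent treatment. The larger count belongs to a death in a dosed child, where attribution solely to ITI is hard to reach. This stands.
- **After dosing, few deaths would fall in the gap.** Criterion 1 needs only possible relatedness, criterion 4 catches any possibly related SAE, and Section 13.10 treats an event as related on any valid suspicion of the product. This stands.
- **The event would not pass unseen.** A reader might infer that such a death could be overlooked or the study simply carry on. The documents do not support that. SAEs are reported within 24 hours from consent (13.9.1.2), the DSMC is notified of all of them (17.1), and a DSMC review precedes each Stage 1 dosing (8.1.1.1). The Table 15 footnote carries the stagger into Stage 2. The weeks between release and dosing also leave time to act.
- **The DSMC Charter may already contain a rule.** This cannot be excluded.
- **Limiting automatic holds to the novel components is defensible.** ITI has its own participant-level rule, and Section 8.3.2 reports that it was well tolerated in two expanded-access participants. That experience is too small to set aside a risk that Section 8.7 calls known.
- **Drawing the line at death is a choice.** A life-threatening SAE attributed only to ITI would still trigger no hold. True, but extending criterion 4 could halt the study for routine immunosuppression SAEs; death is a sensible place to stop.

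None of this supplies an automatic hold in the protocol text. It limits the size of the point.

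**Conclusion.** The omission is real and narrow: a death attributed solely to ITI triggers no automatic suspension under 9.4. What is missing is the certainty of a pause; detection and the means to intervene are already there. The conclusion rests on the protocol text alone, on reading AXO-AAV-GM2 as Table 18 defines it, and on release following the table footnotes. A Charter rule covering the event would reduce the point to a consistency check. No event rate is claimed, because the documents give none. This is a cheap improvement of low to moderate priority.

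**What to change.** 1. In 9.4 criterion 1, add *or the protocol-mandated ITI regimen* as a third source of relatedness, counted from the first ITI dose.
2. State that a hold triggered this way also covers starting ITI in a child who has not begun it. Section 9.4 now suspends only enrollment and vector administration, so an enrolled child could still start the regimen.
3. Name ITI in the post-trigger DSMC review in 9.4.
4. List ITI as a source of relatedness in 13.10, so that the criterion can be applied.
5. Leave criteria 2 to 4 and the participant-level rule in 8.2 unchanged, and check that the DSMC Charter agrees.

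The cost is a few words in two sections and one added relatedness source on the adverse event form; events are already collected from consent. The existing suspension and review are reused. The downside is a rare, short pause after a child's death.

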- Dosing of subsequent participants will only occur after satisfactory DSMC and Sponsor review of 4-week safety data from the previously dosed participant as well as accumulated safety data from all previously dosed participants in the trial. In the Mid and High dose cohorts, after the DSMC has reviewed the 4-week safety data from the first (Juvenile) participant, an infantile and second Juvenile participant may be treated concurrently.

An additional participant may be entered at any dose level if a participant is lost to follow-up or experiences $a \ge Grade 3$ related AE before 4 weeks post-gene transfer. Each staggered participant may start limited screening activities, as detailed in the schedule of assessments for juveniles (Table 14) and infants (Table 15), respectively. The rest of the study assessments can be pursued only once the DSMC and Sponsor approve the dosing of additional participants.

Gene transfer will be administered over the course of two days (Section 11.5) as follows:

- At Visit 1a/Day 1, participants will receive bilateral intraparenchymal infusions of AXO-AAV-GM2 into the thalamus (BiTh)
- At Visit 1b/Day 2, participants will receive ICM/IT infusion of AXO-AAV-GM2 into the CSF

All AXO-AAV-GM2 infusions will be comprised of a 1:1 mixture of rAAVrh8-*HEXA* and rAAVrh8-*HEXB*.

To ensure venous access and ability to draw protocol specified safety labs, as well as reduce the pain associated with difficult blood draws during the study, a central venous catheter may be inserted with caregiver consent prior to surgical gene transfer.

Following gene transfer, Stage 1 juvenile participants will be assessed for safety and efficacy over a 2-year period, during which they will undergo safety, biomarker, neurocognitive, neurologic and motor function assessments according to Table 14. Stage 1 infantile participants will undergo safety, biomarker, neurologic and motor function assessments according to Table 15 over a 1-year period. Neurologic and motor function assessments may be videotaped.

Confidential Page 6 of 97

UMass Chan Medical School

Clinical Study Protocol: AXO-GM2-001

Version 8.0, 09 June 2023

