8.1.1.1. Stage 1 – Dose Escalation

Stage 1 dosing consists of a Starting Dose, Low Dose, Mid Dose, and High Dose (Figure 6). The first participant enrolled in the study can be either sub-type (infantile or juvenile) and will be administered the Starting Dose. Prior to dosing of each participant, the independent DSMC must review the available safety data from all previous participants and make a recommendation regarding continued enrollment and dose escalation. Additional participants beyond those planned in a cohort may be dosed, for example, if requested by the DSMC or regulatory agency, or if a participant within a dose level cohort is lost to follow up or experiences a ≥ Grade 3 related AE before 4 weeks post-gene transfer.

Requirements for dose escalation or progression to Stage 2 of the study are as follows:

1. DSMC recommendation to continue as planned, and:

Confidential Page 38 of 97

[figure not shown]
Clinical Study Protocol: AXO-GM2-001

Version 8.0, 09 June 2023

• At the Low Dose: at least 4 weeks of safety data are available from 2 juvenile and 1 infantile participant administered the Low Dose.

- For the Mid Dose and High Dose:
 - At least 4 weeks of safety data from at least 1 juvenile participant and 2 infantile participants are required to dose escalate.
 - In addition, dose escalation of juvenile participants may also occur based on at least 4
 weeks of safety data from at least 2 juvenile participants and may occur prior to infantile
 dose escalation.

Figure 6: Stage 1 Dose Escalation Scheme

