13.4. Laboratory Assessments

Laboratory assessments for safety will be performed by the site's local laboratory, and all certification/qualification documentation will be on file in the TMF. A laboratory test result should be assessed as clinically significant or not clinically significant, and should be reported as an AE if it meets any of the following criteria:

- Accompanied by clinical symptoms
- Results in a medical intervention or a change in concomitant therapy
- Clinically significant in the investigator's judgement

If a clinically significant laboratory abnormality is a sign of a disease or syndrome (e.g., hemoglobin below the lower limit of normal associated with anemia), only the diagnosis should be recorded. If the abnormality is not a sign of a disease or syndrome, the abnormality itself should be recorded (e.g., low calcium).

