13.11. Recording Adverse Events

Adverse events spontaneously reported by the participant and/or in response to an open question from the study personnel or revealed by observation will be recorded during the study at the investigational site. Clinically significant changes in laboratory values, blood pressure, and pulse need not be reported as AEs. However, abnormal values that constitute an SAE or lead to discontinuation of administration of study drug must be reported and recorded as an AE. Information about AEs will be collected from the signing of consent until the end of the LTFU. Serious Adverse Event information will be collected from the signing of consent form until the end of the LTFU. The AE term should be reported in standard medical terminology when possible. For each AE, the investigator will evaluate and report the onset (date and time), resolution (date and time), intensity, causality, action taken, serious outcome (if applicable), and whether or not it caused the participant to discontinue the study.

AE intensity will be assessed according to NCI CTCAE v5.0.

It is important to distinguish between serious and severe AEs. Severity is a measure of intensity whereas seriousness is defined by the criteria under Section 13.9.1.2. An AE of severe intensity may not be considered serious.

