17. STUDY COMMITTEES

17.1. Independent Data and Safety Monitoring Committee (DSMC)

The DSMC is an independent multidisciplinary group (independent of both the sponsor and CRO) who collectively has experience in the management of participating participants as well as in the conduct and monitoring of clinical trials.

The DSMC will meet at regular intervals allowing for the timely review of 4-week safety data for Stage 1 participants (see Section 8.1.1). The DSMC and Sponsor will determine whether enrollment of participants may proceed according to the dose-escalation plan (Table 10). Based on satisfactory review of 4-week safety data for each participant, accrued safety data of all participants, and review for potential safety signals related to AXO-AAV-GM2 as well as that of the neurosurgical administration/infusion procedures, the DSMC may recommend to continue the study as designed, to continue the study with modifications (e.g. dose descalation/escalation in the event of toxicity), or to terminate the study early based on the safety.

After the last Stage 1 participant has been dosed and observed for 4 weeks, the DSMC will review the cumulative safety data in conjunction with the Sponsor and determine the optimal AXO-AAV-GM2 dose regimen to be administered in Stage 2. The DSMC will continue to meet at regular intervals throughout the duration of the study.

The DSMC will review enrollment progress, baseline characteristics of the study population, all treatment-emergent safety reports, clinical laboratory and imaging data. The members of the DSMC will be notified of all SAEs.

Additional details regarding the specifics of the DSMC operations may be found in the DSMC Charter.

Confidential Page 89 of 97

Version 8.0, 09 June 2023

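### Stopping criterion 3 counts related Grade 3+ events within one child, so recurrence of a non-serious event across children forces no suspension; section 13.11 also conflicts with 13.4 and 13.1 on which events can count

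*Combined protocol and SAP*

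**What the plan says.** Section 9.4 lists four events, any one of which temporarily suspends enrolment and dosing:

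1. a death at least possibly related to the product or procedure;
2. a related intracranial haemorrhage, or an event suggesting craniospinal herniation;
3. "Two or more CTCAE Grade 3 or higher adverse events in any participant that are assessed by the investigator", where the assessment is of at least a possible relation to the product or procedure;
4. any SAE, in any participant, judged related in the same sense.

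Section 13.11 separates severity from seriousness: "An AE of severe intensity may not be considered serious".

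On DSMC review, the Synopsis says for Stage 1 that "Dosing of subsequent participants will only occur after satisfactory DSMC and Sponsor review of 4-week safety data from the previously dosed participant", together with accumulated data. Section 8.1.1.1 adds: "Prior to dosing of each participant, the independent DSMC must review the available safety data from all previous participants". In the Mid and High cohorts, an infantile and a second juvenile participant may be treated concurrently once the first juvenile's data have been reviewed. Section 17.1 ties the 4-week review to Stage 1 participants, then says "The DSMC will continue to meet at regular intervals throughout the duration of the study" and "The members of the DSMC will be notified of all SAEs". Section 8.1.2 places Stage 2 under Table 15 and mentions no stagger. A Table 15 footnote describes 4-week staggered enrolment subject to DSMC and Sponsor review, without limiting it to Stage 1.

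On what becomes an AE, section 13.4 has each laboratory finding judged clinically significant "or not clinically significant, and should be reported as an AE if it meets any of the following criteria": symptoms, an intervention or change in therapy, or clinical significance in the investigator's judgement. Section 13.1 sets the same rule for vital signs. Section 13.11 says "Clinically significant changes in laboratory values, blood pressure, and pulse need not be reported as AEs", except for values that constitute an SAE or lead to discontinuation of study drug administration.

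**The concern.** The same toxicity appearing in different children is one of the main signs that the dose or the procedure is causing it. For non-serious Grade 3+ events, section 9.4 makes suspension mandatory when two fall in one child, but leaves recurrence across children to judgement. In the extreme, ten children with one such event each would not force a pause, while one child with two would. Gene transfer cannot be undone (section 9.3), so holding the next dosing is the main protection that a stopping rule can offer.

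The reporting conflict adds to this. An abnormality that is never recorded as an AE cannot count towards criterion 3, and it is also absent from the Stage 1 primary endpoint, the incidence and severity of TEAEs.

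**Working it through.** **Step 1: which events are left to criterion 3.** Criterion 4 suspends on a single related SAE, and the SAE definition in 13.9.1.2 is broad: it includes prolonged hospitalisation and events significant in the investigator's judgement. Criteria 1 and 2 act on a single event. What remains is an event that is related, Grade 3 or higher, not serious and not named in criterion 2. Criteria 3 and 4 both use the singular *any participant*. In criterion 4 this plainly means one child, which favours reading criterion 3 as a count within one child. The AESIs in 13.9.1.3, which that section equates with dose-limiting toxicities, are not referred to in 9.4.

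**Step 2: when DSMC review covers the gap.**

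| Situation | Review before the next dosing? |
|---|---|
| Stage 1, event seen by the 4-week review | Yes (Synopsis, 8.1.1, 8.1.1.1), but no count is set |
| Stage 1, concurrent pair | Not between the two children |
| Stage 2, if the Table 15 footnote applies | Yes, again with no count |
| Stage 2, if it does not apply | Regular meetings, interval not stated; event-level notice of SAEs |
| Late event in a child already reviewed | At the next review |

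Late events are plausible: prednisolone tapering starts at Week 12 and sirolimus weaning at Week 24 (section 8.2).

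**Step 3: the reporting rules side by side.** Sections 13.4 and 13.1 make clinical significance sufficient for AE reporting. Section 13.11 says such changes need not be reported unless serious or leading to discontinuation of administration. For a non-serious Grade 3 laboratory abnormality after a one-time dose, the two rules give opposite answers.

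**Step 4: illustration of a two-child rule.** The plan states no operating characteristics and no toxicity rate, so there is no figure to reproduce. The rates below are assumptions. Suppose one event type occurs at most once per child, independently, with probability p. The chance that at least two of n children are affected is

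A(n, p) = 1 − (1 − p)^n − n p (1 − p)^(n−1).

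For n = 10 and p = 0.10: 1 − 0.3487 − 0.3874 = 0.264. Criterion 3 as written cannot fire in this setting, by construction.

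| p | Pause at any time, 10 children: A(10, p) | Before child 10, event known at once: A(9, p) | Before child 10, known one child later: A(8, p) |
|---|---|---|---|
| 5% | 0.09 | 0.07 | 0.06 |
| 10% | 0.26 | 0.23 | 0.19 |
| 20% | 0.62 | 0.56 | 0.50 |
| 30% | 0.85 | 0.80 | 0.74 |

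In a 3-child Stage 1 level dosed one at a time, the rule acts before the third child only with probability p²: 0.01, 0.04 and 0.09 at 10%, 20% and 30%.

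**Step 5: relaxing one event per child.** Let events per child be Poisson with assumed mean λ, for 10 children. Write a = e^(−λ) and b = λe^(−λ). Criterion 3 as written fires with probability 1 − (a + b)^10. The chance that two or more children have exactly one event each and none has two, so that criterion 3 stays silent, is (a + b)^10 − a^10 − 10 b a^9.

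| λ | Criterion 3 fires | Two or more children affected, criterion 3 silent |
|---|---|---|
| 0.1 | 0.05 | 0.22 |
| 0.2 | 0.16 | 0.43 |
| 0.3 | 0.31 | 0.49 |
| 0.5 | 0.61 | 0.35 |

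**Step 6: restarting the count.** If the count ran over all 22 planned children (12 + 10), the chance of at least one pause would be A(22, p) = 0.30, 0.66 and 0.95 at 5%, 10% and 20%. If it restarts at Stage 2, the chance of a pause in either stage is 1 − [1 − A(12, p)][1 − A(10, p)]. With A(12, p) = 0.118, 0.341 and 0.725, that gives 0.19, 0.51 and 0.90.

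**The case against.** The strongest reply is that little is left uncovered. The remaining events must be related, Grade 3+, non-serious, outside criterion 2 and at most one per child. Children are inpatients after infusion, so many periprocedural Grade 3 events would prolong the stay and trigger criterion 4 at once. A 9.4 suspension leads to DSMC review, and under the stagger dosing already waits for satisfactory DSMC review. Section 17.1 also has the DSMC review all treatment-emergent safety reports and clinical laboratory data, so an abnormality not recorded as an AE can still reach it. All of this stands, and it is why the gap is narrow.

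Two further points stand in part. Criterion 3 could be meant as a pooled count, since the lead-in speaks of events occurring in the study. The parallel with criterion 4 makes that less natural, and the same rewording would settle it. The DSMC Charter was not available and may add guidance, but 9.4 is where mandatory suspension is defined.

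A reader might infer that Stage 2 children would be dosed without participant-by-participant review. The documents do not support that: Table 15 governs Stage 2, and its footnote is not restricted to Stage 1. Nor do they establish the opposite, because 8.1.2 is silent and 17.1 ties the 4-week review to Stage 1. The Stage 2 stagger is simply unclear.

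**Conclusion.** The point holds, within limits. On its more natural reading, criterion 3 does not mandate suspension when the same related, non-serious Grade 3+ event recurs across children, and no other criterion does. In practice this matters mainly for late events between reviews, and for Stage 2 if the 4-week stagger does not apply there. DSMC review covers most of the rest, as a judgement without a set count. The contradiction between 13.11 and sections 13.4 and 13.1 does not depend on how criterion 3 is read.

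The probabilities might be taken as the number of children spared harm. They are not: the rates and independence are assumed, and DSMC review, the main safeguard, is not modelled. They show how a two-child rule would behave and how often it would pause the trial. The change is worth making because it is cheap and the treatment is irreversible; the documents do not show that the present safeguards would fail.

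**What to change.** (a) Reword criterion 3 as: 'two or more related Grade 3 or higher AEs in any one participant, or the same or a medically similar related Grade 3 or higher AE in two or more participants'. Keep the present definition of related: possibly, probably or definitely, to the product or the neurosurgical procedure. State that the count restarts after each DSMC review that clears resumption, and at the start of Stage 2. Align the DSMC Charter, including who decides what is medically similar.

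(b) Replace the exempting sentence in 13.11 with the reporting rule of 13.4 and 13.1, so that clinically significant laboratory and vital-sign changes are recorded as AEs and count towards criterion 3.

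The drafting cost is one clause with its restart rule, one reconciled sentence and an aligned Charter. The operating cost is some extra temporary pauses, each ending in a DSMC review; Steps 4 and 6 show how often at assumed rates. A long pause could cost a child eligibility. The only stated infant window, 6 to 20 months at gene transfer, is written for Stage 1 (section 9.1), so these reviews should be convened promptly.
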